## VI.6 How many minor subjects do you expect to consent or enroll for this project?

### VI.13 Describe EACH of your subject populations

- Include description of any control group(s)
- Specify the Inclusion/Exclusion criteria for EACH group

A total of 30 healthy men and women ages 18-49 years who are obese defined as body mass index (BMI) of 30 kg/m2 or greater and with prediabetes (defined as fasting blood glucose between 100-126 mg/dl, a fasting blood glucose of 140-199 mg/dl at 120 min during an oral glucose tolerance test; or HbA1C of 6-6.5%) will be enrolled and randomized to 4-5 weeks of salsalate or placebo in the study. CONTROL GROUP: Another n=10 healthy obese men and women age 18-49 WITHOUT prediabetes will be enrolled for baseline testing but will not undergo randomization to the salsalate/placebo intervention. Therefore, total enrollment will be n=40.

All subjects will have no history of cardiovascular, metabolic or pulmonary disease as determined from medical history and physical exam, and a resting 12-lead ECG. Subjects may be on anti-hypertensive medications but will be asked to hold the medication on the morning of testing. Subjects on medications for Type I or II diabetes mellitus or for hyperlipidemia will be excluded (see complete list below). Subjects will be non-smokers or quit smoking at least one year ago. Women will have regular menses and will be tested during the early follicular phase of their menstrual cycle (within 8 days of onset of menses) to control for differences in circulating estradiol concentrations.

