# VII.D.27 Discuss how much time a potential subject will have to agree to consider participation and whether or not they will be able to discuss the study with family/friends before deciding on participation.

There is no time limit for the subject to agree to consider to be in the study as long as the study is actively recruiting subjects. Subjects are allowed to discuss the study with family/friends before deciding on participation.

VII.D.28 How long after the subject agrees to participate do study procedures begin?

Screening tests can begin on the same day as consent (Visit 1). The subject will return for an additional screening visit (Visit 2) within 1 week or less. The

experimental procedures will be completed within 1-2 weeks of Visit 2.

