#### **DESCRIBE:**

- What subjects will be asked to do/what happens in the study (in sequential order)
- The time period over which procedures will occur
- The time commitment for the subject for individual visits/procedures
- Long-term followup and how it occurs

Experimental design. A total of 30 obese (defined as body mass index >30 kg/m2) adults age 18-49 years with prediabetes will be enrolled and randomized to 4-5 weeks of Salsalate or placebo in a randomized (2:1), double-blind, placebo controlled, parallel study design. Subjects will orally ingest 3000 mg/day (1500 mg in a.m. and 1500mg in the p.m.) of Salsalate (n=20) or placebo (n=10) for 28-35 days. A total of n=10 obese NON-prediabetic CONTROL subjects will be enrolled to establish prediabetes-related differences in obese adults primary outcomes at baseline. Therefore, a total of 40 subjects will be enrolled. The non-prediabetic control subjects will undergo screening (Visits 1 and 2) and baseline experimental testing (Visits 3, 4) but will NOT undergo the Salsalate/placebo intervention or visits 5, 6 or 7. Prediabetes will be defined as fasting (at leaset 8 hour fast) blood glucose between 100-126 mg/dl, a fasting blood glucose of 140-199 mg/dl at 120 min during an oral glucose tolerance test, or HbA1C between 6.0 – 6.5%.

Order of visits. Subjects will undergo experimental testing at baseline and again after the 4-5 weeks of Salsalate or placebo. Subjects will be studied between 7:00 and 10:00 am in the Clinical Research Unit (CRU) in the Institute for Clinical and Translational Science (ICTS) at the University of Iowa following an 8 hour overnight fast. The order of visits are as follows and will occur over a period of 7-8 weeks (see TABLE 1 attachment for summary of visits):

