#### Visit 1 (3.5 hours): Consent and Screening

- a. Explanation of the study; reading and signing of written informed consent b. If subject consents but requires a 2-week washout for aspirin, salicylate, NSAID, vitamin, supplements, they will be scheduled to complete the Visit 1 in 2 weeks. If subject consents and no washout is needed, screening tests will be performed same day to determine eligibility by the following:
- i. Research staff will obtain resting vitals (blood pressure, heart rate)
- ii. Research staff will obtain anthropometrics including weight, height, waist and hip circumference with tape measure.
- iii. Research staff will obtain resting 12-lead ECG
- iv. Subject will fill out the Demographics and Health History survey, and the Modified Activity Questionnaire (MAQ)
- v. Research nurse or trained staff will obtain venous blood draw using butterfly needle for UIHC pathology labs:
- Creatinine, Lipid panel, TSH(4.5 ml blood- 1 light green PST tube)
- Complete blood count(4.5 ml blood- 1 lavender tube)
- Subject will undergo oral glucose tolerance test (OGTT): Subject will consume a beverage containing 75 grams of glucose. Blood samples will be collected at timed intervals of baseline, 1 hour and 2 hours after consuming beverage for glucose and insulin. Total blood collected for insulin and glucose for OGTT: 13.5 ml blood (4.5ml x 3 PST tubes).
- TOTAL blood collected for Visit 1: 22.5 ml (1.5 Tablespoons)

- Visit 2 (2 hours): Dietary food record, cerebral blood flow velocity
- a. Meet with CRU bionutritionist for instruction on 3-day dietary record to return on visit 3
- b. Middle cerebral artery blood flow velocity using transcranial dopper during the following protocol to measure cerebral vasoreactivity to hypercapnia:
- -After 3 min of normal breathing, subjects will perform 2, 30 second breathholds sparated by 3 min.
- -Next, After 3 min of room air breathing, 3 min of breathin 2%CO2, 3 min of breathing 4%CO2 (balanced with 21%O2 and N) will be performed followed by 3 min of room air breathing.
- c. Subject will be instrumented with 24 hour blood pressure monitor to wear home for 24 hours. Subject will return it to the investigators when come in for Visit 3. There is no long term follow up.
- Visit 3 (3 hours): 1st Baseline experimental visit (Blood, Endothelial cells, FMD, PWV and Retina scan)
- a. Subject arrives at the CRU between 7-10 am after overnight 8 hour fast

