- b. Subjects on vasoactive medications will be asked to hold medication on the morning of experimental visits but to bring the medications with them to be taken after the visit.
- c. Return 3-day dietary recall
- d. IV catheter, endothelial cell collection and blood sample: Subject will lie supine and research nurse will insert venous 18 G catheter into antecubital vein.
- e. Research staff or physician will perform J wire endothelial cell collection (3 wires) via 18 G catheter.
- f. After 20 min, nurse practitioner will then obtain blood samples thru catheter:
- Lipid panel, insulin, hs-CRP, salicylate, creatinine, AST/ALT (4.5 ml blood- light green PST tube)
- Catecholamines (8 ml blood- 2 x 4 ml Na+ Hep green top tubes)
- HbA1c (4.5 ml blood- 1 x 4.5 ml lavender top tubes)
- Extra blood collected for specialized labs performed in PIs lab:

Serum: 17 ml blood-  $2 \times 8.5$  red/gray top SST tube) for interleukin-6, tumor necrosis factor-alpha.

Whole blood (17 ml blood-  $3 \times 8.5$  ml Citrate PPT tube) for mononuclear cell DNA isolation.

- f. After 15 min supine rest the following non-invasive vascular measurments are obtained by the PI and his research staff:
- 1) Radial, brachial, carotid and femoral waveforms non-invasively for PWV assessment
- 2) Carotid artery compliance using ultrasonography
- 4) Brachial artery flow-mediated dilation (FMD) with ultrasound
- 5) Brachial artery dilation after 0.3 mg sublingual nitroglycerin with ultrasound
- g. Subject escorted to the CRU Human Cardiovascular Research Lab and a physician or research staff trained in microneurography will insert needle into peroneal nerve for measurement of muscle sympathetic nerve activity
- h. Subject will meet with bionutritionist and review 3-day food record with subject
- i. Subject receives meal/snack from CRU bionutrition and then can leave
- \*\*TOTAL blood collected for Visit 3= 68 ml (~4.5 tablespoons)

Visit 4 (4.5 hours): 2nd Baseline experimental visit (Forearm Blood Flow and Microneurography)

- a. Subject comes to the CRU Human Cardiovascular Research Lab in the CRU between 7-10am after 8 hour overnight fast
- b. Subject will be instrumented with upper arm venous occlusion cuffs and wrist cuffs

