for measurements of forearm blood flow using venous occlusion plethysmography c. A physician trained in brachial artery catheterization in the Human Cardiovascular Research Lab will then perform brachial artery catheterization with 27 G needle and undergo incremental infusions of saline, acetylcholine, acetylcholine + vitamin C (ascorbic acid), and sodium nitroprusside + vitamin C (see Expermental Procedures for details)

- d. Subject will be escorted to Dept of Ophthalmology in Pomerantz Bldg and have picture of retinal performed (scan takes  $\sim$ 10 min)
- e. Subject will be given snack or lunch in CRU.
- f. Subjects will be randomized in a 2:1 scheme to Salsalate or placebo
- g. Nurse will dispense 35 day supply (210 tablets) of Salsalate (dose 3000 mg/day = 500 mg tablets x  $6/\text{day} \times 35 \text{ days} = 210 \text{ tablets}$ ) or placebo
- h. Subject will take first dose of Salsalate (500 mg x 3 pills) or placebo at CRU and 2nd dose (1500 mg) at home in evening- this is Day 0

Visit 5 (45 min) ~Day 14: Subject will return to CRU for venous blood sample to measure serum salicylate (4.5 ml x 2 PST tubes: total 9 ml or ~0.5 tablespoons), Blood pressure, HR and survey of any side effects. If any side-effects/symptoms present, nurse coordinator will follow instructions as outlined in section VIII.2 "Plan for Managing Risks". Subject will receive 3-day food record booklet from CRU bionutritionist

Days 25: Coordinator or research staff will call subject in the evening to remind subject to start 3-day dietary record on days 26, 27, 28.

Visit 6 (5 hours) Betwee Day 26-34: Post-experimental visit #1 (FMD, PWV and Retina)

- a. Subject will take morning dose of Salsalate/placebo and return to CRU between Day 26 -35 for venous blood sample to measure serum salicylate, blood pressure, HR; and survey of any side effects
- b. All vascular measurements of Visit 3 will be repeated
- c. Middle cerebral artery blood flow velocity using transcranial dopper during the following protocol to measure cerebral vasoreactivity to hypercapnia:
- -After 3 min of normal breathing, subjects will perform 2, 30 second breathholds sparated by 3 min.
- -Next, After 3 min of room air breathing, 3 min of breathin 2%CO2, 3 min of breathing 4%CO2 (balanced with 21%O2 and N) will be performed followed by 3 min of room air

breathing.

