- d. Subject escorted to the CRU Human Cardiovascular Research Lab and a physician or research staff trained in microneurography will insert needle into peroneal nerve for measurement of muscle sympathetic nerve activity
- e. Subject will be instrumented with 24 hour blood pressure monitor to wear home for 24 hours. Subject will return it to the investigators when come in for Visit 7. There is no long term follow up.

Total blood collected for visit 6: 68 (~4.5 Tablespoons)

Visit 7 (3 hours) Between Day 27-35: Post-experimental visit #2

- a. Subject will take morning dose of Salsalate/placebo return to CRU on Day 27 or 28 for venous blood sample to measure serum salicylate, AST/ALT and creatinine (0.5 ml blood)
- b. All measurements from Visit 4 will be repeated
- c. Blood draw for salicylate, insulin, lipid panel, creatinine, ALT/AST (1  $\times$  4.5 ml lt green PST tube)
- d. Total blood collected for visit 7: 4.5 ml ( $\sim$ 1/3 tablespoon)

GRAND TOTAL Blood drawn over course of study: 172 ml (~11.5 tablespoons)

Screening Methods.

- a) Blood pressure, ECG. Subject will undergo resting BP in a private CRU exam room after 15 minutes of rest. BP will be measured in supine position in triplicate separated by 2 min with an automated oscillometric BP machine under quiet, comfortable laboratory conditions. All BPs throughout study will be performed in this identical manner. A resting supine 12-lead ECG will be recorded by placing 10 electrodes on chest and recording the ECG.
- b) History and Physical exam. Prior to the experimental visit (Visit 3), subjects will undergo a complete medical history and physical examination by [name] or a CRU nurse practitioner.
- c) Blood chemistries: After passing the physical exam standard blood chemistry analysis will be obtained under fasting conditions including a basic metabolic panel, lipid panel, HbA1C, complete blood count, TSH and FSH (for women only).

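### Cerebral CO2 reactivity and 24-hour blood pressure: on the visit-step wording the medication hold covers follow-up (Visit 6) but not baseline (Visit 2), and the sections conflict on which visits the hold and cycle-phase rules cover

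*Combined protocol and SAP*

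**What the plan says.** **Where the measurements are taken.** The visit list in VII.E.6 has the entry "Visit 2 (2 hours): Dietary food record, cerebral blood flow velocity". The same visit's step c says "Subject will be instrumented with 24 hour blood pressure monitor to wear home for 24 hours", and the device comes back at the next visit: "Subject will return it to the investigators when come in for Visit 3". Follow-up for both is under "Visit 6 (5 hours) Betwee Day 26-34: Post-experimental visit #1 (FMD, PWV and Retina"), steps c and e, with the monitor returned at Visit 7.

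**How the visits are labelled.** VII.D.28 says "The subject will return for an additional screening visit (Visit 2) within 1 week or less". The design paragraph of VII.E.6 says of the non-prediabetic controls that they "will undergo screening (Visits 1 and 2) and baseline experimental testing (Visits 3, 4"). Section VIII.2 (scheduled safety visit) calls Visits 6 and 7 experimental.

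**The two rules on conditions.**
- Medication hold, VII.E.6, Visit 3 step b: "Subjects on vasoactive medications will be asked to hold medication on the morning of experimental visits". The drugs are brought along and taken after the visit.
- Medication hold, VI.13: antihypertensives are permitted and held on the morning of *testing*. No visit is named.
- Cycle phase, VI.13: women "will be tested during the early follicular phase of their menstrual cycle (within 8 days of onset of menses"). No visit is named.

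**The methods text.** Cerebral reactivity is described under the heading for Visit 3 methods, and ambulatory blood pressure under the heading for Visit 4 methods.

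**The analysis (XI.1).** The treatment-by-time interaction is the critical test. Pre versus post contrasts for salsalate and for placebo, and Pearson correlations of changes, are also planned.

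**The concern.** A pre/post change is interpretable only if both measurements are made under the same conditions. If staff follow the visit steps, a participant on an antihypertensive has taken the morning dose before the baseline CO2 test and has not taken it before the follow-up test.

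The 24-hour record is affected in a milder way. The hold delays the dose rather than omitting it, but at follow-up the delayed dose falls near the start of the recording. Visit 7 may be the next morning and would delay the following dose inside the same recording. At baseline neither delay occurs.

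If Visit 2 is also outside the cycle-phase rule, many women would have baseline and follow-up in different phases. VI.13 gives control of estradiol as the reason for that rule, so the protocol itself treats phase as something to hold constant.

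The order of testing also differs. Visit 6 lists the CO2 test after the repeated Visit 3 vascular measurements, which include sublingual nitroglycerin; Visit 2 lists none of these.

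At stake is the meaning of the within-arm changes, and of the change correlations, for these two outcomes.

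**Working it through.** The plan states no figure on this point, so there is none to reproduce. The check sets the sections side by side, counts schedules, and traces the effect on each planned analysis.

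**1. Coverage of the rules**

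| | Visit 2 (baseline) | Visit 6 (follow-up) |
|---|---|---|
| Label | Screening (VII.D.28; VII.E.6 design) | Experimental (VIII.2) |
| Hold, Visit 3 step b wording | Not covered | Covered |
| Hold, VI.13 wording | Could be covered | Could be covered |
| Cycle phase, VI.13 | Not named | Not named |
| Nitroglycerin earlier in the visit | None listed | Listed in step b, before the CO2 test |

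Only the second row separates the two visits on the wording of a rule.

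**2. Cycle phase, if Visit 2 is exempt**

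Inputs:
- The window is taken as cycle days 1–8 (VI.13).
- Visits 3 and 4 are on separate days, both in the window (assumption).
- Visit 4 is at most 14 days after Visit 2 (VII.D.28, upper limit of 1–2 weeks).
- Visit 3 is at least 3 days after Visit 2. This is inferred: the food record is taught at Visit 2 and kept for the 3 days before Visit 3.

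Let *c* be the cycle day of Visit 3, *k* the days from Visit 3 to Visit 4 (1 to 7), and *g* the days from Visit 2 to Visit 3.

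- Permitted schedules: each *k* allows (8 − k) values of *c* and, with g ≥ 3 and g + k ≤ 14, (12 − k) values of *g*. Sum of (8 − k)(12 − k) = 77 + 60 + 45 + 32 + 21 + 12 + 5 = **252**.
- Visit 2 is in the window when c − g ≥ 1, which gives (c − 3) values of *g* and (8 − c) of Visit 4 for c = 4 to 7: 1×4 + 2×3 + 3×2 + 4×1 = **20**. 20/252 = 7.9%.
- With a 1-day minimum gap: sum of (8 − k)(14 − k) = 91 + 72 + 55 + 40 + 27 + 16 + 7 = **308**. In the window: sum of (c − 1)(8 − c) for c = 2 to 7 = 6 + 10 + 12 + 12 + 10 + 6 = **56**. 56/308 = 18.2%.

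**3. Can Visit 6 meet the window?**

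Visit 4 is Day 0 and Visit 6 is Day 26–34. With an assumed cycle of *L* days, the cycle day at Visit 6 is (Visit 4 cycle day) + (study day) − L. For L = 28, Visit 4 on cycle day 2 leaves Days 27–34, and on cycle day 8 leaves Days 26–28. For L = 24, no day remains if Visit 4 was on cycle day 7 or 8 (for example 7 + 26 − 24 = 9). So Visit 6 can usually comply, but no section says that it must.

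**4. Effect on the analyses**

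Let *p* be an arm's share on vasoactive drugs and *h* the mean shift from holding at follow-up only. Let *w* be the share of women whose phase differs and *m* the corresponding shift. Assume *h* and *m* are the same in both arms.

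- Within-arm change is off by p·h + w·m.
- The interaction is off by (p_sals − p_plac)·h + (w_sals − w_plac)·m, which is zero on average under randomisation.
- With 20% attrition, completers are 20 × 0.8 = 16 and 10 × 0.8 = 8. One more drug user moves *p* by 1/16 = 6.25 points in the salsalate arm and by 1/8 = 12.5 points in the placebo arm, so chance imbalance is easy.

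The documents as available give none of *p*, *w*, *h* or *m*, so the shift itself cannot be sized.

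**The case against.** The strongest reply is that VI.13 already settles the matter. Both rules attach to *testing*, and a CO2 challenge is plainly a test. The lists of screening procedures (VII.D.26, and the screening methods in VII.E.6) include neither measurement, and the methods text treats both as experimental. If the methods headings governed, the baselines would sit at Visits 3 and 4 and the mismatch would largely vanish. A visit table is also mentioned as an attachment and is not available here.

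Much of this stands. A reader might infer that the protocol exempts Visit 2 from both rules and places Visit 6 under both. The documents do not say so: the hold mismatch follows from one wording and not from the other, and for cycle phase no section exempts Visit 2 or names Visit 6.

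It does not remove the point. The visit steps are what staff carry out, and Visit 2 contains no hold. The methods headings are not a dependable guide to placement either: the item under Visit 4 methods that describes 24-hour pressure also covers baroreflex sensitivity, which its own text assigns to Visits 3 and 6. If VI.13 does cover Visit 2, Visits 2, 3 and 4 must all fit within 8 days, whereas VII.D.28 allows up to two weeks.

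The reply that randomisation protects the comparison is right for the interaction. It does not cover the within-arm contrasts.

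**Conclusion.** The point holds as a conflict between sections with a conditional consequence. The visit schedule pairs a Visit 2 baseline with a Visit 6 follow-up, and the wording of Visit 3 step b applies the hold to the second and not the first. If Visit 2 is handled as screening, within-arm changes and change correlations for cerebral reactivity and 24-hour blood pressure mix treatment with medication timing in every user of vasoactive drugs, and possibly with cycle phase in women.

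The 8% and 18% figures hold only under that reading. They weight all permitted schedules equally and should not be read as the chance that a given woman is in phase.

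A reader might also conclude that the estimated salsalate effect is biased. The documents do not support that: both arms follow the same schedule, so the interaction is unbiased on average and suffers only extra variance and possible chance imbalance at 20 versus 10. Neither outcome is named in the Aims (I.5), and the stated primary outcome is carotid-femoral pulse wave velocity (XI.2). The change is worth making because it is cheap, not because the main result depends on it.

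**What to change.** Take the baseline of both measurements at Visit 3, which agrees with the methods heading for cerebral reactivity, so that baseline mirrors Visit 6:

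- Fit the baseline monitor at the end of Visit 3 and collect it at Visit 4, at least 24 hours later, as Visits 6 and 7 do at follow-up.
- Fix the position of the CO2 test relative to nitroglycerin and make it identical at Visits 3 and 6.
- Record the time of the last antihypertensive dose before each measurement.
- Reconcile VI.13, VII.D.28, and the design, visit steps and methods headings of VII.E.6, naming the visits that each rule covers. Medication and cycle-phase conditions must be the same before and after. How medication is handled is for the clinicians to decide.

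**Cost.** No new visit or procedure. Visit 3, listed at 3 hours, becomes longer and Visit 2 shorter. The CO2 sequence in the visit steps takes 3 + 0.5 + 3 + 0.5 + 3 + 3 + 3 + 3 = 19 minutes of recording; the documents give no time for probe placement or monitor fitting. Visit 4 can no longer be less than 24 hours after the monitor is fitted.

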#### Planned Use in this Study

Condition/Disease Indication(s)

Subject Population Obese adults 18-49 with prediabetes

Dose(s) 25 mg/min intra-arterial infusion

Administration Other: Intra-arterial via brachial artery

Vascular dysfunction

Dosing Regimen Intra-brachial infusion at 25 i

Intra-brachial infusion at 25 mg/min at rate of 1 ml/min for a 10 minute. Then, co-infused with acetylcholine for 6 min at 3 mcg/min, 6 min at 30 mcg/min. After a 20 min washout, intra-brachial artery infusion at 25 mg/min at a rate of 1 ml/min for 10 minutes and co-infused with sodium nitroprusside at rate 1 ml/min for 6 min at 1 mcg/min and then 6 min at 10 mcg/min.

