Drug infusion protocol: First, baseline FBF responses to intra-brachial artery infusions of 0.9% saline will be measured for 20 min at rate of 1 ml/min. Next, FBF responses during intra-brachial artery infusions of 2 incremental doses of the endothelial agonist acetylcholine (Ach; doses 3 and 30 mcg/min) or the endothelium-independent agonist sodium nitroprusside (SNP; doses 1 and 10 mcg/min) at 1 ml/min will be performed for 6 min for each dose. Both drugs will be diluted in 0.9% saline and sequence of Ach and SNP will be randomly assigned. FBF from each drug infusion will be recorded during the 3rd to 6th minute of each dose. A washout period of 0.9% saline at 1 ml/min will be performed for 20 min or less if FBF returns to baseline sooner. Next, the effects of oxidative stress on EDD will be determined by measuring the effect of ascorbic acid (vitamin C) infusion (25 mg/min) at an infusion rate 1 ml/min for a 10 minute loading dose prior to ACh infusion, and then continuous infusion throughout incremental infusion of AcH (doses 3 and 30 mcg/min). Specifically, any difference in the FBF response to ACh and the FBF response to ACh + vitamin C can be attributed to a reduction in vascular oxidative stress. SNP is used as an NO donor to test endothelium-independent dilation to establish that any observed group differences in Ach-mediated vasodilation is due, at least in part, to stimulated endothelial NO release per se, and not impairments in smooth muscle vasodilator function to an NO donor. Note: The concentrations selected for each of these agents have been shown to elicit changes in FBF without affecting systemic hemodynamics (i.e., no changes in heart rate or blood pressure).

b) Microneurography. Direct intra-neural recordings of sympathetic activity to skeletal muscle will be obtained using microneurography, as previously described. A tungsten micro electrode (200  $\mu$ m diameter shaft; 1-5  $\mu$ m uninsulated tip) is inserted into the peroneal nerve posterior to the head of the fibula. Well-validated criteria are used to

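### The forearm infusion session is described in two incompatible versions, and each leaves one acetylcholine response without a nitroprusside response under the same vitamin C condition

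*Combined protocol and SAP*

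**What the plan says.** Three places in the combined protocol and SAP describe the intra-arterial session.

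- **VII.E.6, Visit 4 step c** lists saline, acetylcholine, "acetylcholine + vitamin C (ascorbic acid), and sodium nitroprusside + vitamin C" and adds "see Expermental Procedures for details". Nitroprusside appears only together with vitamin C.
- **V.8, ascorbic acid entry, Dosing Regimen** gives vitamin C for 10 minutes, then with acetylcholine at two doses of 6 minutes each. After a 20-minute washout there is a second 10-minute vitamin C infusion, and vitamin C is then "co-infused with sodium nitroprusside at rate 1 ml/min for 6 min at 1 mcg/min", followed by 6 minutes at the higher dose.
- **VII.E.6, Experimental Methods for Visit 4, Drug infusion protocol** starts with saline, then acetylcholine and nitroprusside, both without vitamin C. For nitroprusside it reads "endothelium-independent agonist sodium nitroprusside (SNP; doses 1 and 10 mcg/min) at 1 ml/min will be performed for 6 min for each dose", and the "sequence of Ach and SNP will be randomly assigned". After a washout, vitamin C is loaded for 10 minutes and continued through a second acetylcholine run. There is no nitroprusside plus vitamin C step.

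The Drug infusion protocol also states the inferences. "SNP is used as an NO donor to test endothelium-independent dilation", so that group differences in the acetylcholine response can be assigned to the endothelium and not to smooth muscle. Any difference between acetylcholine with and without vitamin C is to be read as the effect of reducing oxidative stress.

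The Visit 7 plan repeats the Visit 4 measurements. VII.B.11 answers that no separate written protocol exists.

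**The concern.** A control infusion does its job only if it is given under the same conditions as the response it controls. Whether nitroprusside is infused with or without vitamin C decides which acetylcholine response it can be set against, and the plan answers that question in two ways.

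Forearm plethysmography is one of the planned measures of resistance-vessel function, before and after treatment and between the prediabetic and non-prediabetic groups. If the sequence that is run does not match the stated inference, part of that inference has no control. If different subjects or visits follow different texts, their responses are not comparable. An infusion that was not given cannot be recovered at analysis.

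**Working it through.** The plan gives no sample size, power or alpha figure on this point, so the check is a comparison of texts plus one dose total.

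**Step 1. Conditions in each description**

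| Condition | Visit 4 step c | V.8 ascorbic acid entry | Drug infusion protocol |
|---|---|---|---|
| Acetylcholine alone | yes | outside its scope | yes |
| Acetylcholine + vitamin C | yes | yes | yes |
| Nitroprusside alone | no | outside its scope | yes |
| Nitroprusside + vitamin C | yes | yes | no |

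The V.8 entry covers only infusions that contain vitamin C, and both of its conditions are in the Visit 4 list. Those two places agree. The Drug infusion protocol differs from the Visit 4 list in both nitroprusside rows. That makes two versions, told in three places.

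**Step 2. Matched pairs** (acetylcholine and nitroprusside under the same vitamin C condition)

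- Visit 4 list: the pair with vitamin C is present; the pair without vitamin C is missing.
- Drug infusion protocol: the pair without vitamin C is present; the pair with vitamin C is missing.

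Each version lacks one pair, and each gap touches a stated inference. Under the Visit 4 list, the response to acetylcholine alone cannot be checked against smooth-muscle function under the same condition. Under the Drug infusion protocol, nothing shows whether vitamin C altered the smooth-muscle response to a nitric oxide donor, so assigning the whole vitamin C effect to oxidative stress is not fully controlled.

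**Step 3. Do the other drug entries in V.8 settle it?** The acetylcholine entry lists each dose twice, which fits two acetylcholine runs in either version. The nitroprusside entry lists each dose once and does not mention vitamin C, which fits one nitroprusside run in either version. They do not decide between the two. The single nitroprusside run also speaks against combining both versions into one longer session. These entries give acetylcholine and nitroprusside doses per mL per minute, whereas the ascorbic acid entry and the Drug infusion protocol give them per minute.

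**Step 4. Vitamin C total per session**, at 25 mg/min. For the Drug infusion protocol I assume that the 6 minutes per dose stated for its first block also applies to the vitamin C run.

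- Drug infusion protocol: 10 + 6 + 6 = 22 min; 22 × 25 = 550 mg.
- V.8 ascorbic acid entry: 2 × (10 + 6 + 6) = 44 min; 44 × 25 = 1100 mg.

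The ratio is 1100 / 550 = 2. The same V.8 entry lists 300-1000 mg/day as the approved dose, so 1100 mg is 100 mg above the top of that range and 550 mg lies inside it. V.6 answers that all drugs are used within the approved dose. On the V.8 regimen, the document contradicts its own figures.

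**The case against.** The strongest reply is that Visit 4 step c is a visit summary that defers to the detailed procedures, and those procedures include nitroprusside without vitamin C. On that view the detail governs and the control for acetylcholine alone is present. This has weight: staff who follow the pointer will run the Drug infusion protocol. It does not remove the conflict. The V.8 entry has no such pointer and sets out nitroprusside plus vitamin C with its own washout, loading period and doses, so the Visit 4 wording is not an isolated slip. The detailed text also does not elaborate the list: it drops one listed condition and adds another.

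A second reply is that Visit 7 repeats Visit 4, so each subject should receive the same sequence twice. That is the evident intent, and nothing in the documents shows that staff would switch. It does not say which sequence is to be repeated.

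Several stronger readings are tempting, and the documents do not support them:

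- That there are three different sequences. The V.8 entry is a subset of the Visit 4 list.
- That the Visit 4 list imposes a fixed order against the random one. It is a list of infusions and says nothing about whether the order is fixed.
- That under the Visit 4 list no endothelial claim could be made for any of the 40 subjects. The pair with vitamin C is matched there; only acetylcholine alone lacks its counterpart.
- That forearm blood flow is the main microvascular measure. No section says so, and VII.E.6 also has a retinal microvascular assessment.

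**Conclusion.** The inconsistency is real and should be corrected. There are two incompatible versions, and neither supports everything that the Drug infusion protocol infers: one lacks a matched control for acetylcholine alone, the other for acetylcholine plus vitamin C. Planned vitamin C exposure differs twofold between them (550 or 1100 mg per session), and the larger total conflicts with the approved range and the V.6 answer as the document gives them.

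The ambiguity covers the planned 40 subjects at Visit 4 and the 30 randomised subjects at Visit 7. Its practical effect depends on which text staff follow, which the documents do not show. XI.2 names carotid-femoral pulse wave velocity as the primary outcome and sizes the trial on it, so no sample size or power figure changes. This is an internal inconsistency in a measure that did not size the trial. It does not threaten the main analysis.

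**What to change.** The sponsor should reconcile V.6, the V.8 entries for nitroprusside, acetylcholine and ascorbic acid (planned regimen, dose units and listed approved dose), Visit 4 step c and the Drug infusion protocol into one sequence. This review does not say which regimen is right. The same sequence should apply wherever the test is performed: Visit 4 for all subjects and Visit 7 for the randomised subjects.

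XI.1 should then state which acetylcholine and nitroprusside responses are compared, and the inferences about smooth muscle and oxidative stress should be limited to what the chosen sequence can support.

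The cost is a wording amendment. All the agents and visits are already planned, and the sample size is unaffected. It should be settled before further sessions are run.
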